**Ethics code: 8970**

## **STUDY DESIGN AND PLAN**

The study will follow a randomised, double-blind, placebo-controlled, parallel groups design.

## **STUDY PROCEDURES**

Testing will take place in a suite of testing facilities with participants visually isolated from each other. Participants will attend the laboratory on 3 separate occasions, an introductory visit between 1 and 14 days before the first day of treatment, and two testing days (Day 1 and Day 29):

[figure not shown]
The Introductory visit to the laboratory will comprise: briefing on requirements of the study, obtaining of informed consent, health screening, completion of the Caffeine Consumption Questionnaire (CCQ) and State-Trait Anxiety Inventory (STAI) trait subscale, training on the cognitive and mood measures and collection of demographic data.

For the two ensuing laboratory-based testing sessions (Day 1, Day 29) participants will attend the laboratory before 8.00 am having consumed a standardised breakfast of cereal and/ or toast at home no later than an hour before arrival. They must have refrained from alcohol for 24 hours and caffeine for 18 hours. On arrival on each day participants will complete the State-Trait Anxiety Inventory (STAI) state subscale and the computerised cognitive assessment (as per Figure 1) followed by measurements of blood-pressure and heart rate. Immediately following this they will consume their treatment for that day. Two further cognitive assessments (plus BP and HR), identical to the pre-dose assessment will commence at 120- (~11:00 am) and 240 (~02:00 pm) minutes post-dose; the latter in order to take advantage of natural declines in performance during the day. Participants will be given a standardised lunch at approximately 12:10 pm. This lunch will comprise a white bread cheese sandwich, packet of ready salted crisps and custard pot.

[figure not shown]
Cognimapp mobile phone assessments will take also place outside of the laboratory before the treatment period begins (Day -6 to -1) and at intervals of 7 (+/- 1 day) days (e.g. Day 7, 14, 21, 28) with the final assessment taking place the day before the final laboratory visit. Assessments will take place in the morning (pre-dose) and evening on each day.

Participants will be prompted by text messaging. Additionally, on Day 24, participants will complete the learning phase of the location-learning task. On day 28 the Cognimapp assessment will include completion of the retrieval phase of the location-learning task.

[figure not shown]
Figures 2 and 3 depict the laboratory-based testing session timeline and chronic study overview respectively.

**Figure 1. The running order of the individual cognitive assessments.** Tasks are shown in order of completion with approximate timings. On the left the 'cognitive domain' assessed by the task is shown and the boxes to the right show potential global measures into which data from several tasks can be collapsed.

**Figure 2. Testing session timeline on both the acute and chronic visit.** participants complete a full cognitive assessment pre-dose and at 120 and 240 mins post-dose. Lunch is provided at approximately 12:10 pm.

**Figure 3. Overall trial diagram.** Diagram includes screening/ training and main acute (day 1) and chronic (day 29) lab visit sessions. Weekly (day -6 to -1, 7, 14, 21 and 28) completion of the mobile phone battery and location-learning task completion (presented during day 25 and retrieved during day 29; with the intervening 3 days representing the memory decay phase) is also depicted.

#### *Treatment schedule across the study*

Participants will be provided with at least 30 days supply of the study's investigational products (sage or placebo) for consumption daily between testing visits Day1 and Day 29 and will undergo the cognitive/mood assessment on the first day (Day 1) and the last day (Day 29) of the active treatment period. The allocation to treatments will be undertaken via a randomly generated treatment schedule.

Details of the mood assessments, COMPASS battery, CDB battery and mobile phone battery are presented in Appendices I, II, III and IV.

## PLANNED ANALYSES

### Cognitive task data, mood scale and Blood Pressure (BP) analysis

The cognitive task, mood and BP measures produce data that can be analysed to assess both acute (potential treatment effects within day 1 and day 29), pure-chronic (chronic treatment-related effects which have taken place across the 29 day supplementation period but prior to taking the day 29 treatment) and superimposed acute/chronic (the difference in 'acute' effects between day 1 and day 29 or the difference in effects pre and post-dose on day 29) effects of treatment. In order to adequately analyse the 'acute', 'pure chronic' and 'superimposed acute/chronic' effects of the treatments the following proposed analyses will be conducted:

#### 1. Pure acute effects

To ascertain if any acute treatment effects have taken place, post-dose data from day 1 and day 29 will be baseline adjusted with regards the pre-dose baseline data collected on day 1 and entered into a two way (treatment x assessment [120/240 min]) ANOVA.

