#### 2. Pure chronic effects

To ascertain if any pure chronic treatment effects have taken place, pre-dose data on day 29 will be baseline adjusted with respect to day 1 pre-dose baseline data and analysed via ANOVA to compare performance between treatments.

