#### 3. Acute, and superimposed effects

- i) To ascertain if any acute effects on day 1 have increased or attenuated over the 29 day treatment period, data from day 1 and day 29 will be baseline adjusted with respect to the respective day's baseline assessment and entered into a three way (day x assessment x treatment) ANOVA.
- ii) To ascertain if there are differential chronic effects pre and post-dose on day 29, pre and post dose data from day 29 will be baseline adjusted with respect to the pre-dose baseline on day 1 and subjected to a two way ANOVA (treatment x assessment).

The proposed a priori and post-hoc comparisons between treatment means to be utilised will be specified in the Statistical Analysis Plan

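### The 'pure acute' analysis refers Day 29 post-dose data to the Day 1 baseline, so a chronic effect can be reported as acute

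*Protocol*

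**What the plan says.** The opening paragraph of the planned analyses (Protocol, Cognitive task data, mood scale and Blood Pressure analysis) separates three kinds of effect. Two matter here:

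- Acute: "acute (potential treatment effects within day 1 and day 29".
- Pure chronic: "chronic treatment-related effects which have taken place across the 29 day supplementation period but prior to taking the day 29 treatment".

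The numbered analyses then fix a baseline for each question:

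- **Analysis 1, Pure acute effects.** Its purpose is "To ascertain if any acute treatment effects have taken place". The method is that "post-dose data from day 1 and day 29 will be baseline adjusted with regards the pre-dose baseline data collected on day 1". The model has treatment and assessment (120/240 min) as factors and no day factor.
- **Analysis 2, Pure chronic effects.** "pre-dose data on day 29 will be baseline adjusted with respect to day 1 pre-dose baseline data".
- **Analysis 3(i).** Its purpose is "To ascertain if any acute effects on day 1 have increased or attenuated over the 29 day treatment period". Each day is adjusted to its own pre-dose assessment and the data are "entered into a three way (day x assessment x treatment) ANOVA".
- **Analysis 3(ii).** "pre and post dose data from day 29 will be baseline adjusted with respect to the pre-dose baseline on day 1". The stated target is differential chronic effects.

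The section leaves to the SAP only which a priori and post-hoc comparisons between treatment means will be used. The baseline reference for analysis 1 is set in the protocol itself.

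**The concern.** A within-day effect on Day 29 is the change from before to after that day's dose. Measured from Day 1 pre-dose instead, the Day 29 post-dose value also contains everything that happened over the supplementation period. The protocol says as much elsewhere: analysis 2 treats the shift from Day 1 pre-dose to Day 29 pre-dose as the chronic effect, and 3(ii) uses the same Day 1-referenced Day 29 post-dose values to look for chronic effects. The same adjusted values are thus called acute in one analysis and chronic in another.

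Analysis 1 is the one whose stated question is whether acute effects occurred at all. If a chronic effect exists, which the trial is set up to look for, this analysis can report it as acute. A chronic effect in the opposite direction can hide a real acute one.

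**Working it through.** **What analysis 1 estimates.** Let A1 and A29 be the within-day treatment effects, and C the treatment difference already present at Day 29 pre-dose. Under randomisation the expected treatment differences are:

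| Time | Expected difference |
|---|---|
| Day 1 pre-dose | 0 |
| Day 1 post-dose | A1 |
| Day 29 pre-dose | C |
| Day 29 post-dose | A29 + C |

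Referred to Day 1 pre-dose, the treatment effect is:

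- days pooled with equal weight: [A1 + (A29 + C)]/2 = (A1 + A29)/2 + C/2;
- Day 29 analysed alone: A29 + C;
- Day 1 analysed alone: A1, which is clean.

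With A1 = A29 = 0 the first two give C/2 and C. With A1 = A29 = 0.15 and C = -0.3 the pooled result is (0.15 + 0.15 - 0.3)/2 = 0, and a real acute effect disappears. ANCOVA gives the same expectations, because the Day 1 baseline precedes all treatment and cannot carry information about C. The same holds for treatment comparisons at 120 or 240 min. If C is equal at both times, the treatment by assessment interaction is unaffected.

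With each day's own baseline subtracted, the pooled effect is [A1 + (A29 + C - C)]/2 = (A1 + A29)/2, so C cancels.

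**Root cause.** The baseline is the fault. Adding a day factor alone would let the days be told apart but would leave C in the treatment main effect.

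**How often this would mislead (illustrative).** The protocol gives no sample size, variance, significance level or expected C, so everything below is assumed. Model: subject, day-within-subject and residual variances s, d, e summing to 1; outcome averaged over 120 and 240 min; no acute effect; two-sided 5%; noncentral t. Change-score variances per participant:

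- pooled as written: d/2 + 1.25e
- Day 29 post-dose minus Day 1 pre-dose: 2d + 1.5e
- Day 1 on its own baseline: 1.5e
- own-day mean over both days: 0.75e

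Worked case, (s, d, e) = (0.60, 0.15, 0.25), 50 per arm, C = 0.5, pooled: variance 0.075 + 0.3125 = 0.3875; standard error √(2 × 0.3875/50) = 0.1245; noncentrality 0.25/0.1245 = 2.01; rejection rate 51.1%. A simulation of 20,000 trials gave a mean effect of 0.251 and rejection in 50.8%.

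Rejection rates (%) at 50 per arm:

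| s / d / e | Pooled change, C = 0.1 | 0.2 | 0.3 | 0.5 | Pooled ANCOVA, C = 0.5 | Day 29 alone, change, C = 0.5 |
|---|---|---|---|---|---|---|
| .60/.15/.25 | 6.8 | 12.5 | 22.2 | 51.1 | 64.0 | 85.4 |
| .70/.10/.20 | 7.4 | 14.8 | 27.3 | 61.8 | 71.4 | 93.8 |
| .50/.10/.40 | 6.3 | 10.2 | 17.0 | 38.6 | 55.1 | 79.0 |
| .40/.10/.50 | 6.0 | 9.3 | 14.8 | 32.5 | 52.3 | 71.9 |
| .50/.25/.25 | 6.6 | 11.6 | 20.2 | 46.5 | 61.8 | 75.4 |
| .80/.05/.15 | 8.4 | 18.9 | 36.4 | 76.6 | 82.3 | 99.1 |

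At C = 0.5, pooled change scores give 18% to 47% with 25 per arm and 57% to 97% with 100 per arm. In simulation under three of the structures, own-day subtraction over both days rejected in 4.9% to 5.1% of trials, and so did the analysis 1 interaction.

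**The case against.** The strongest reply is that the plan already contains the right analysis. Section 3 is headed as covering acute as well as superimposed effects, 3(i) uses each day's own baseline, and its treatment main effect is free of C. Analysis 2 would also tend to expose the problem: in the same model (50 per arm, C = 0.5) it detects C in 62% to 98% of trials with change scores and 77% to 98% with ANCOVA. In every assumed structure that exceeds the rate at which pooled analysis 1 gives a false acute result.

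This limits the damage but does not remove it. The stated purpose of 3(i) is whether Day 1 acute effects changed over time; whether acute effects occurred is given to analysis 1. A significant analysis 2 shows that C exists but does not correct the estimate in analysis 1. If Day 29 is analysed alone, analysis 1 is more likely than analysis 2 to be significant, so the reassurance fails there.

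A second reply is that the Day 1 baseline is the only untreated one and was chosen deliberately. Day 29 then yields a total effect, acute plus chronic, which is a legitimate quantity but not what the heading or the protocol's definition describes.

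It is also fair that the rejection rates depend wholly on assumed inputs; only the bias of C/2 or C is firm.

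**Conclusion.** The point holds and should be fixed. As written, analysis 1 does not estimate the acute effect that the protocol defines: its treatment effect is off by C/2 with the days pooled equally, or by C for Day 29 alone. That result rests only on randomisation and on the Day 1 baseline preceding treatment. The error is zero if C is zero and small if C is small. Over the six assumed structures at 50 per arm, pooled change scores give a false acute finding in 6% to 8% of trials at C = 0.1 SD and 33% to 77% at C = 0.5 SD. The Day 1 component is sound, the interaction is sound when C is constant across the two assessments, and the data collected can answer the question.

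**What to change.** In analysis 1, delete the reference to Day 29, so that Day 1 post-dose data are compared with the Day 1 pre-dose baseline. In 3(i), add that its treatment main effect answers whether acute effects occurred over both days, and that its treatment contrast within Day 29 gives the Day 29 acute effect. Alternatively, merge analysis 1 into 3(i), which already has the required structure. Keep Day 1-referenced Day 29 data for analyses 2 and 3(ii).

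The protocol or SAP should also say that own-day adjustment on Day 29 is by subtraction. The Day 29 pre-dose value is itself affected by treatment; as a covariate with slope b below 1 it leaves (1 - b)C in the estimate. With b = s + d, running from 0.50 to 0.85 over the six structures, that is 0.15C to 0.50C.

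**Cost.** Wording only; no new data or model. With change scores, the Day 1-only contrast has 0.86 to 1.11 times the variance of the pooled contrast as written; with ANCOVA, 1.05 to 1.34 times. Day 1 alone has twice the variance of the own-day mean over both days (0.375 against 0.1875 at 0.60/0.15/0.25), but 3(i) already supplies that mean. On Day 1, where the baseline precedes treatment, ANCOVA remains valid, and subtraction there would have 1.11 to 1.50 times its variance, so subtraction need not be imposed on analysis 1.

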#### 2. Pure chronic effects

To ascertain if any pure chronic treatment effects have taken place, pre-dose data on day 29 will be baseline adjusted with respect to day 1 pre-dose baseline data and analysed via ANOVA to compare performance between treatments.

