### Mobile phone battery analysis

Data will be baseline adjusted and analysed by ANOVA (treatment (placebo and active) by day (7, 14, 21 and 28) by time (am and pm).

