### State Trait Anxiety Inventory (STAI)

Trait anxiety scores, collected during the screening/training visit will be compared between the treatment conditions to ensure that no differences exist between groups on this stable anxiety factor.

State anxiety scores, collected prior to pre-dose cognitive tasks on day 1 and on day 29, will be converted into a change score (day 29 score minus day 1) and compared between treatments via ANOVA.

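### Overall treatment comparisons would be more precise, at no cost, if the pre-treatment score entered the model as a covariate instead of being adjusted out before an ANOVA

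*Protocol*

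**What the plan says.** All references are to the Protocol, Planned Analyses.

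- **1. Pure acute effects:** post-dose data are "baseline adjusted with regards the pre-dose baseline data collected on day 1 and entered into a two way (treatment x assessment [120/240 min]) ANOVA"; this covers both testing days.
- **2. Pure chronic effects:** "pre-dose data on day 29 will be baseline adjusted with respect to day 1 pre-dose baseline data and analysed via ANOVA".
- **3. Acute, and superimposed effects, (i):** data are "baseline adjusted with respect to the respective day's baseline assessment and entered into a three way (day x assessment x treatment) ANOVA".
- **3(ii):** Day 29 pre- and post-dose data are adjusted to the Day 1 pre-dose value and go into a treatment-by-assessment ANOVA.
- **Mobile phone battery analysis:** "Data will be baseline adjusted and analysed by ANOVA", with treatment, day and time as factors.
- **State Trait Anxiety Inventory (STAI):** state scores are "converted into a change score (day 29 score minus day 1) and compared between treatments via ANOVA".

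No covariate is named anywhere, and *baseline adjusted* is not defined. The end of section 3 leaves to the SAP only the a priori and post-hoc comparisons between treatment means. The document gives no correlation, standard deviation, sample size, alpha or power.

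**The concern.** The listed analyses adjust the data first and then fit a model without baseline in it. If the adjustment is subtraction, the slope of follow-up on baseline is fixed at 1. Under randomisation any fixed slope gives a valid comparison, but the most precise one uses the slope that the data support. With equal variances that slope is rho, which is below 1. The change score then carries avoidable baseline noise into every overall comparison of sage with placebo. At stake is power that the collected data could supply without any extra measurement.

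**Working it through.** **Inputs.** From the Protocol: two arms, randomised parallel groups; one follow-up value in analysis 2 and for state anxiety; two post-dose values per day (120 and 240 min) in analysis 1; three Day 29 values in 3(ii); eight phone values (four days, am and pm). Assumed: equal variances (set to 1) and a common correlation rho between all assessments, 0.5 to 0.9. The Protocol has no figure of its own to reproduce.

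**Formulas.** For the treatment main effect on the mean of k follow-up values with one baseline value:

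- variance of the mean: V = (1 + (k-1)rho)/k
- change score: V + 1 - 2rho
- ANCOVA: V - rho²

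The difference between the last two is (1 - rho)², which is never negative. For k = 1 the ratio ANCOVA/change is (1 - rho²)/(2(1 - rho)) = (1 + rho)/2.

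**Results** (ANCOVA variance / change-score variance = ratio):

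| rho | k = 1 (analysis 2, state anxiety) | k = 2 (analysis 1, one day) | k = 3 (main effect in 3(ii)) |
|---|---|---|---|
| 0.5 | 0.75/1.00 = 0.75 | 0.50/0.75 = 0.67 | 0.417/0.667 = 0.63 |
| 0.7 | 0.51/0.60 = 0.85 | 0.36/0.45 = 0.80 | 0.310/0.400 = 0.78 |
| 0.8 | 0.36/0.40 = 0.90 | 0.26/0.30 = 0.87 | 0.227/0.267 = 0.85 |
| 0.9 | 0.19/0.20 = 0.95 | 0.14/0.15 = 0.93 | 0.123/0.133 = 0.93 |

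A simulation with an estimated slope (60 per arm, chosen for illustration; 5,000 replicates) gave change/ANCOVA ratios of 1.35 at rho 0.5 and 1.18 at rho 0.7, against 1.33 and 1.18 from 2/(1 + rho).

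**Phone battery.** With k = 8 and one baseline value the ratio is 0.31/0.56 = 0.56 at rho 0.5, 0.2475/0.3375 = 0.73 at 0.7, 0.185/0.225 = 0.82 at 0.8 and 0.1025/0.1125 = 0.91 at 0.9. If am is adjusted to am and pm to pm, the main effect uses the mean of two baselines. Its variance is B = (1 + rho)/2, so change = V + B - 2rho and ANCOVA = V - rho²/B. At rho 0.7 this gives 0.161/0.1875 = 0.86. The gain is smaller but in the same direction.

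**Power, for scale.** Assume a two-sided 0.05 test with 80% power on change scores. With ANCOVA on the same participants, power is Φ((1.96 + 0.84)/√ratio - 1.96). For k = 1 this is 90%, 86%, 84% and 82% at rho 0.5, 0.7, 0.8 and 0.9. For k = 2 it is about 93% at rho 0.5 and 85% at rho 0.8.

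**Interactions.** Subtracting the same baseline B from both assessments gives (Y240 - B) - (Y120 - B) = Y240 - Y120, so B cancels. The correlation of that contrast with B is proportional to rho - rho = 0, so a covariate has nothing to explain. The same holds for treatment-by-day in the phone battery.

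**Analysis 3(i).** The Day 29 pre-dose score is measured after about four weeks of treatment. Let c be a chronic effect already present at that point and a the acute effect. Subtraction gives (c + a) - c = a. Using that score as a covariate with slope rho gives c + a - rho·c = a + c(1 - rho). With c = 0.3 SD and rho = 0.7 (both assumed) the error is 0.3 × 0.3 = 0.09 SD.

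**The case against.** **The term is undefined.** A reader might infer that the Protocol prescribes change scores for every outcome. It does not say so. Only state anxiety is expressly turned into a change score, and the different wording elsewhere could mean percentage change or a covariate. An SAP not at hand may define it. This stands as a limit: subtraction is the natural reading of adjusting data and then entering them into an ANOVA without a covariate, but it is an inference. A covariate meaning used throughout would not settle the matter either, because in 3(i) it would condition on a post-randomisation score.

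**The analysis is valid.** A reader might infer bias from chance imbalance at Day 1. Given a baseline difference D between arms, the change-score estimate is off by -(1 - rho)D, but this averages to zero over randomisation and its variance is already in the change-score standard error. It is the (1 - rho)² term in the working, not a second harm.

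**Not every test gains.** A reader might infer that all the acute, chronic and phone tests lose power. The interaction tests do not under the assumed correlation structure, and that includes the question 3(ii) poses, whether effects differ before and after the Day 29 dose. Nor is 3(i) an instance of the weakness: within-day subtraction estimates what it asks.

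**The size is unknown.** No correlation is given. At rho 0.9 the saving for a single follow-up is only 5% of participants.

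**Conclusion.** The point holds as an efficiency improvement that costs nothing, not as an error. It applies to the overall treatment comparisons in analyses 1 and 2, the main effect in 3(ii), the phone battery and state anxiety. For state anxiety it rests on explicit text; for the others it rests on reading the adjustment as subtraction. On the assumed equal variances and common correlation of 0.5 to 0.9, the covariate analysis has 0.75 to 0.95 of the change-score variance for a single follow-up. For the mean of two post-dose values it has 0.67 to 0.87 at rho 0.5 to 0.8. The direction holds for every rho below 1; the size depends on a figure that the document does not give. Since the document designates no main outcome, the point cannot be tied to a primary result.

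**What to change.** Replace the undefined term with a stated model:

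- **Analyses 1, 2 and 3(ii):** analyse the observed scores with the Day 1 pre-dose score as a covariate; do not subtract it first.
- **Phone battery:** analyse the observed scores with the pre-treatment phone score as a covariate, and say which score that is (for example, the one from the same time of day).
- **State anxiety:** analyse the Day 29 score with the Day 1 score as a covariate.
- **Analysis 3(i):** state that the adjustment is within-day subtraction. Do not use the Day 29 pre-dose score as a covariate.

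The cost is a wording change in the Planned Analyses and a matching line in the SAP. It needs no new data and no change to study procedures. It should be settled before unblinding.

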#### 3. Acute, and superimposed effects

- i) To ascertain if any acute effects on day 1 have increased or attenuated over the 29 day treatment period, data from day 1 and day 29 will be baseline adjusted with respect to the respective day's baseline assessment and entered into a three way (day x assessment x treatment) ANOVA.
- ii) To ascertain if there are differential chronic effects pre and post-dose on day 29, pre and post dose data from day 29 will be baseline adjusted with respect to the pre-dose baseline on day 1 and subjected to a two way ANOVA (treatment x assessment).

The proposed a priori and post-hoc comparisons between treatment means to be utilised will be specified in the Statistical Analysis Plan

